#### **Visit 5: Week 12 (plus or minus 5 calendar days)**

The research nurse will telephone call the participant and undertake the following assessments:

- GAD-7
- EQ-5D-5L
- WASA
- PHQ-9
- Athens Insomnia Scale
- CSRI
- Check treatment compliance and anxiety log completion (if continuing with Alpha-Stim AID CES treatment)
- Check adverse events (if continuing with Alpha-Stim AID CES treatment)

The research nurse will administer these and record the data either directly into the electronic patient record (PCMIS) if available (and therefore the PCMIS record will act as source data), or into a Case Report Form (CRF) if not available (and therefore the CRF will act as source data) and then transpose the data into PCMIS or scan the CRF into the electronic file.

It is anticipated that these assessments will take approximately 45 minutes in total.

At this visit, the participant will end treatment with Alpha-Stim AID CES and the research nurse will ask that they return the medical device via post.

The final treatment session should be completed immediately prior to the visit 5 assessments undertaken by the research nurse.

#### **Visit 6: Week 24 (plus or minus 5 calendar days)**

The research nurse will telephone call the participant and undertake the following assessments:

- GAD-7
- EQ-5D-5L
- CSRI

- WASA
- PHQ-9
- Athens Insomnia Scale

The research nurse will administer these and record the data either directly into the electronic patient record (PCMIS) if available (and therefore the PCMIS record will act as source data), or into a Case Report Form (CRF) if not available (and therefore the CRF will act as source data) and then transpose the data into PCMIS or scan the CRF into the electronic file.

It is anticipated that these assessments will take approximately 30 minutes in total.

This is the end of study visit, after which the participant will cease communication with the research nurse.

## 7.6 Assessment summary

ASSESSMENT	VISIT 1 DAY 1	VISIT 2 WEEK 4	VISIT 3 WEEK 6	VISIT 4 WEEK 8	VISIT 5 WEEK 12	VISIT 6 WEEK 24
CONSENT	X					
TRAINING IN USE OF ALPHA STIM AID	X					
PREGNANCY TEST	X (*)					
GAD-7	X	X	X	X	X	X
EQ-5D-5L	X	X	X	X	X	X
CSRI	X				X	X
WASA	X	X	X	X	X	X
PHQ-9	X	X	X	X	X	X
ATHENS	X	X	X	X	X	X
ALPHA-STIM AID CES TREATMENT	Ongoing	Ongoing	Ongoing (**)	Ongoing (**)	Ongoing (**)	
COMPLIANCE		X	X	X (**)	X (**)	
ADVERSE EVENTS		X	X	X (**)	X (**)	

(\*) If a female of child-bearing potential

(\*\*) If continuing with Alpha-Stim AID CES treatment between week 6 – week 12.

## 7.7 Follow up

If a participant is unavailable for the pre-arranged telephone call visit, and the visit is likely to fall outside of the 5 calendar day window, the sponsor legal representative must be informed.

If a participant is lost to follow up during the Alpha-Stim AID CES treatment period, or during the follow up period, best efforts should be made to re-establish contact by the research nurse, in conjunction with the IAPT service, to ensure return of the medical device and full data collection.

## **7.8 Withdrawal**

Participants will be made aware that they are free to withdraw from the study at any time point, without giving reason. If participants withdraw during the Alpha-Stim AID CES treatment period, the participant should return the medical device and any unused electrodes to the research nurse. Participants will be informed that the data collected prior to their withdrawal will be retained for analysis unless a specific request is made for their data to be removed from analysis.

Participants may be withdrawn from the study, if it is in the best interests of the participant, in the view of the Principal Investigator.

## **7.9 End of study**

Participants will be enrolled in the study for 24 weeks from baseline, with the recruitment window anticipated to open 01 September 2016 and close 01 March 2017. The end of study is defined as last participant last visit, and this is anticipated at 01 September 2017. The REC will be notified of the end of study.

# **8 STUDY DEVICE**

## **8.1 Nature of device**

The medical device is the Alpha-Stim AID CES device, which will be used within intended purpose (for the treatment of anxiety, depression and insomnia), under CE marking valid 12 April 2016 – 12 September 2020.

*See Appendix H.*

## **8.2 End of study provision**

The device is marketed and sold in the UK by the sponsor legal representative, and are available from private purchase at a cost of £499.00. Participants will be fully informed that participation in the study will result in a maximum of 12 weeks of Alpha-Stim AID device treatment, after which time point the device must be returned to the research nurse. Participants will not be encouraged to purchase a device, but will be advised by the research nurse if an interest is expressed. Participants will not receive a discount on the purchase of a device.

## **8.3 Storage and handling on device**

60 Alpha-Stim AID CES medical devices will be provided to site in one single bulk dispatch, and will be loaned for the period of the study. All 60 medical devices are expected to be returned to the sponsor legal representative by the end of the study. The devices should be kept in secure location until given to participants, for use in their homes, for the 6 or 12 week treatment period. Should all 60 devices be in use by participants concurrently, additional devices may be loaned.

The sponsor is not listed on the NHS Master Indemnity Agreement register, and therefore a Form of Indemnity will be signed between the sponsor as the device supplier and the site to provide confirmation that there is adequate public and product liability insurance in place for £1,000,000.00.

*See Appendix I*

The site will not be held liable for maintenance and cleaning costs, wear-and-tear, accidental damage and loss of these devices.

## **8.4 Safety profile**

CES is the application of a pulsed, mild electrical current to the head using ear clip electrodes (0.5 Hz, 50% duty cycle, and 100 to 500 µA). The U.S. Food and Drug Administration (FDA) cleared CES for the treatment of anxiety, depression and insomnia in 1979. CES is non-invasive and has an excellent safety profile. A FDA commissioned review of the safety of CES by the National Research Council (1974) stated, “significant side effects or complications attributable” to the application of electric current of approximately one milliampere or less for “therapeutic effect to the head” (i.e., cranial electrotherapy stimulation) were “virtually non-existent”. The Alpha-Stim AID uses 50% of this amount of current at the highest CES setting. A review of 14 Alpha-Stim CES studies using human subjects revealed that incidence of adverse events was < 1% and all were mild and self-limiting. Between 2007 and 2011, there was a total of 8,248,920 Alpha-Stim CES treatments (1,982,520 individual users treatments plus 6,266,400 in-office treatments by practitioners) based on the sales figures for 2007 - 2011 of 58,030 minus returns (there were 75 returns in 2011), an individual home Alpha-Stim post-marketing user survey (EPI, 2011a) and an Alpha-Stim practitioner survey (EPI, 2011b).

14 adverse events were reported 2007 – 2011, comprising skin irritation at electrode site (11), tinnitus (2) and panic attack (1).

No serious adverse events have been reported during the 33 years that Alpha-Stim CES had been on the market.

## 9 SAFETY REPORTING

### 9.1 Definitions

Term	Definition
Adverse Event (AE)	Any untoward medical occurrence in a participant receiving treatment with Alpha-Stim AID CES, including occurrences which are not necessarily caused by or related to that product.
Serious Adverse Event (SAE)	A serious adverse event is any untoward medical occurrence that: 
 
• results in death
 
• is life-threatening
 
• requires inpatient hospitalisation or prolongation of existing hospitalisation
 
• results in persistent or significant disability/incapacity
 
• consists of a congenital anomaly or birth defect
 

### 9.2 AE reporting

The purpose of this study is not demonstrate clinical effectiveness of Alpha-Stim AID CES, which has been established. However, AEs should be recorded in PCMIS and reported to the CI or sponsor legal representative via completion of the CRF upon the research nurse becoming aware of these.

### 9.3 SAE reporting

SAEs should be recorded in PCMIS and the CRF, and reported to the CI or sponsor legal representative via telephone and email upon the research nurse becoming aware of these. The CI or sponsor legal representative will notify the REC which issued favourable opinion within 15 days of becoming aware of the event using the HRA SAE report form for non-CTIMPs.

### 9.4 Urgent safety measures

The CI or sponsor legal representative will notify the REC which issued favourable opinion immediately by telephone or within 3 days in writing of the implementation of an urgent safety measure and the plan for further action.

### **9.5 Pregnancy reporting**

A urine pregnancy dipstick human chorionic gonadotropin test will be used to assess pregnancy in all females of child-bearing potential at baseline. Pregnancy should be recorded in PCMIS and reported to the CI or sponsor legal representative via email upon the research nurse becoming aware of these and a decision will be made regarding continued participation.

Pregnancy is an exclusion criterion and reportable as a precautionary measure as research has not been undertaken on the safety and efficacy of Alpha-Stim AID CES treatment in pregnant patients.

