Alpha-Stim AID is a CE marked medical device which has been registered as an approved product since 11 May 1998. Alpha-Stim AID is marketed for the alleviation of psychological conditions including anxiety, insomnia and depression, through using cranial electrotherapy stimulations (CES) which are tiny electric currents applied through ear clips. The treatment provided by the device is non-invasive, non-pharmacological, and can be used as adjunctive treatment to step one, two and three treatment intervention. Pregnancy, implantation with a pace maker and implantation with an implantable cardioverter device (ICD) are contraindications.

Alpha-Stim AID CES could therefore compliment psychological treatment in the IAPT care pathway, through acting as an effective maintenance treatment, and to act as adjunctive treatment to improve the clinical effectiveness of step three high intensity psychological therapy intervention. Improved effectiveness could reduce the requirement for additional psychological and pharmacological treatment, thus reducing cost within the health and social care system (primarily within the IAPT services but also within primary care), thus enabling the IAPT service to maintain capacity to deliver high intensity psychological therapy intervention.

This study will recruit 120 participants from Leicestershire and Rutland IAPT service (under the organisation of Nottinghamshire Healthcare NHS Foundation Trust). These participants will have a primary working diagnosis of moderate-to-severe GAD, and will have received step two low intensity psychological therapy intervention within an IAPT service but received no improvement (continued to be classified as moderate-to-severe GAD) from these interventions.

So as to place the study in the context of a systematic review of relevant studies, the following information provides background to the clinical effectiveness of CES treatment generally, and then specifically for anxiety, depression and insomnia.

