## **6 ELIGIBILITY CRITERIA**

### **6.1 Inclusion criteria**

- Primary working diagnosis of moderate-to-severe GAD indicated via a GAD-7 score of 10 or more at baseline visit
- Previous treatment within an IAPT service with step two low intensity psychological therapy intervention
- Indicated for step three high intensity psychological therapy intervention and on the waiting list OR deemed unsuitable for step two within an IAPT service
- Capable of giving informed consent
- Female participants of child-bearing potential must have a negative urine human chorionic gonadotropin dipstick pregnancy test
- Female participants of child-bearing potential must be practising a highly effective method of contraception (failure rate of less than 1% per year when used consistently and correctly and agree to remain on a highly effective method throughout the 6 or 12 week treatment period. Examples of highly effective contraceptives include: barrier condoms, intrauterine device (IUD), intrauterine hormone-

releasing system (IUS), vasectomised partner, sexual abstinence (refraining from heterosexual intercourse), and oestrogen and progestogen containing hormonal contraception associated with ovulation.

- 18 years of age or above at baseline visit
- Able to understand written and verbal English

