## **6.2 Exclusion criteria**

- Primary working diagnosis of a mental disorder other than moderate-to-severe GAD (but other mental and anxiety disorders as secondary comorbidities is not an exclusion criteria)
- No previous treatment within an IAPT service with step two low intensity psychological therapy intervention
- Not indicated for step three high intensity psychological therapy intervention and not on the waiting list
- Requiring urgent clinical care
- Female participants of child-bearing potential with a positive urine human chorionic gonadotropin dipstick pregnancy test
- Female participants of child-bearing potential not willing to practice a highly effective method of contraception during the treatment period
- Implantation with a pace maker
- Implantation with an implantable cardioverter defibrillator (ICD)
- Incapable of giving informed consent
- 17 years of age or less at baseline visit
- Unable to understand written and verbal English

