## **7.3 Screening**

Participants will have a confirmed working diagnosis of moderate-to-severe GAD via a GAD-7 score of 10 or more upon identification by the PWP or Cognitive Behavioural Therapist as potentially eligible for the study.

Once the ICF has been signed, the research nurse will take a urine pregnancy dipstick test for any female participant of child-bearing potential. Should the result be positive, their involvement will terminate at this time-point and they will continue to receive routine care.

It is possible that, over the timeframe of having been identified and provided consent to participate, the GAD-7 score of the participant may have changed. As such, once the ICF has been signed, the research nurse, trained in the administration of the GAD-7, will undertake a GAD-7 assessment with the participant. Should the participant, at this baseline visit, have a score of 9 or less, their involvement will terminate at this time point and they will

continue to receive routine care. The research nurse will also re-confirm full eligibility in accordance with the inclusion/exclusion criteria.

This baseline visit will be the sole additional in-clinic visit, with all other study visits undertaken via telephone. Patients that attend this baseline visit will have their travel expenses reimbursed up to a maximum of £10.00 and must submit their receipt(s) or indication of miles driven (reimbursement up to £0.45 per mile in accordance with HMRC guidance). Patients will receive this reimbursement in cash at the baseline visit.

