**Visit 3: Week 6 (plus or minus 5 calendar days)**

The research nurse will telephone call the participant and undertake the following assessments:

- GAD-7
- EQ-5D-5L
- WASA
- PHQ-9
- Athens Insomnia Scale
- Check treatment compliance and anxiety log completion
- Check adverse events

The research nurse will administer these and record the data either directly into the electronic patient record (PCMIS) if available (and therefore the PCMIS record will act as source data), or into a Case Report Form (CRF) if not available (and therefore the CRF will act as source data) and then transpose the data into PCMIS or scan the CRF into the electronic file.

It is anticipated that these assessments will take approximately 30 minutes in total.

At this visit, the research nurse will discuss whether the participant wishes to continue with Alpha-Stim AID CES treatment in the same manner for an additional 6 weeks. If the participant does wish to do so, they will be advised that they must continue to complete the anxiety log book. The decision to continue or end treatment with Alpha-Stim AID CES will not impact upon access to stand care therapy interventions, and participants will be contacted by the IAPT service regardless of their decision at this time point. If the participant does not wish to continue with Alpha-Stim AID CES treatment, the research nurse will ask that they return the medical device via post.

The final treatment session should be completed immediately prior to the visit 3 assessments undertaken by the research nurse.

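### Section 9.5 leaves open what follows a pregnancy found during device use, and no contact after Visit 1 is scheduled to ask about one

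*Combined protocol and SAP*

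**What the plan says.** Section 1 (Background) gives the status of pregnancy for this device: "Pregnancy, implantation with a pace maker and implantation with an implantable cardioverter device (ICD) are contraindications". Section 6.2 (Exclusion criteria) carries this into eligibility: "Female participants of child-bearing potential with a positive urine human chorionic gonadotropin dipstick pregnancy test". Section 7.3 (Screening) attaches a fixed consequence at baseline: "Should the result be positive, their involvement will terminate at this time-point and they will continue to receive routine care".

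Section 9.5 (Pregnancy reporting) covers a pregnancy that comes to light later. It is to be recorded and emailed to the CI or the sponsor legal representative "upon the research nurse becoming aware of these", after which "a decision will be made regarding continued participation". The section repeats that pregnancy is an exclusion criterion and calls it "reportable as a precautionary measure as research has not been undertaken on the safety and efficacy" of the device in pregnant patients. It does not refer back to the contraindication in section 1.

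Sections 6.1 and 6.2 require participants of child-bearing potential to use, and agree to stay on, highly effective contraception for the 6- or 12-week treatment period. The stated standard is a failure rate below 1% per year with consistent and correct use. The assessment summary in section 7.6 places the pregnancy test at Visit 1 only. At week 6, section 7.5 says that "the research nurse will discuss whether the participant wishes to continue with Alpha-Stim AID CES treatment in the same manner for an additional 6 weeks".

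**The concern.** The same condition has a definite consequence on day 1 and an open one afterwards. A research nurse who learns of a pregnancy in week 5 finds a contraindication in section 1, termination of involvement in section 7.3 and an unspecified decision in section 9.5. Nothing says what happens to device use in the meantime, or whether the decision concerns the device, the remaining assessments, or both.

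The open wording matters more because the plan has no scheduled step by which a pregnancy would be found. Section 9.5 starts only when the nurse becomes aware. The point where this bears most is week 6, when a further six weeks of home use is offered: every listed step can be completed without the subject coming up. At stake is participant safety in a situation that the protocol itself says has not been researched. Sample size, error rates and the planned summaries are not affected.

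**Working it through.** The plan states no figure on this point, so there is none to reproduce. The check has two parts.

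**1. The passages side by side**

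- *Status of pregnancy.* Section 1: contraindication. Section 6.2: exclusion. Section 9.5: exclusion, reportable as a precaution.
- *Consequence at baseline.* Section 7.3: involvement ends.
- *Consequence later.* Section 9.5: a decision on participation, with no criteria, timing, named decision-maker or interim instruction on the device.
- *Device use and participation are different things in this study.* Under sections 4 and 7.5, a participant may stop the device at week 6 and still be assessed to week 24. A decision on participation therefore does not by itself settle device use.
- *Pregnancy test.* Sections 7.6 and 9.5: baseline only.
- *Calls at weeks 4 and 6 (section 7.5).* Five questionnaires, compliance with treatment and the anxiety log, and adverse events. No pregnancy or contraception item.
- *Calls at weeks 8 and 12.* The same, with the CSRI at week 12, and with the compliance and adverse-event checks only for those still using the device. No pregnancy or contraception item.
- *Week-6 continuation.* It turns on the participant's wish. No re-check of pregnancy status is listed.

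The consequence after baseline is thus undefined, and after Visit 1 the contraception commitment is not scheduled to be checked.

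**2. How often the situation might arise**

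Inputs:

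- N = 120 (section 11.1).
- Device use of 6 weeks, or at most 12 (section 7).
- Annual failure rate r = 0.01, the ceiling in section 6.1.
- Share s of participants of child-bearing potential: not given. Assumed 0.30 to 1.00.

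Formulas: person-years = N × s × weeks/52; expected pregnancies = person-years × r; P(at least one) = 1 − exp(−expected).

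*All participants use the device for 12 weeks:*

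- s = 0.30: 120 × 0.30 × 12/52 = 8.31 person-years; × 0.01 = 0.083 expected; 1 − exp(−0.083) = 8%.
- s = 1.00: 120 × 12/52 = 27.69 person-years; × 0.01 = 0.277 expected; 1 − exp(−0.277) = 24%.

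*All participants use the device for 6 weeks:*

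- s = 0.30: 4.15 person-years; 0.042 expected; 4%.
- s = 1.00: 13.85 person-years; 0.138 expected; 13%.

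The expected count is proportional to r. The 1% ceiling presupposes consistent and correct use, which no later contact is scheduled to confirm.

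**The case against.** The strongest reply is that the plan does protect participants during home use. Contraception is required for the whole treatment period and those unwilling are excluded. Adverse events are checked at every call while the device is in use. Participants are told to contact the nurse with queries, and section 7.8 lets the Principal Investigator withdraw anyone in their best interests. The participant information sheet and the device instruction sheet are not among the pages available, and either may tell participants to report a pregnancy. All of this stands. A reader might infer that the exclusion is unprotected after day 1; the documents do not support that. What remains is narrower: the commitment is made once, no scheduled item checks it, and the adverse-event checks would reveal a pregnancy only incidentally.

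The second reply is that section 9.5 speaks of participation, not device use. It can be read as deciding only whether a pregnant participant stays in follow-up, which would not conflict with section 1. That reading is fair. A reader might infer that section 9.5 permits device use to continue in pregnancy, but the text is silent and does not say so. That silence is why the passages need reconciling.

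Three further inferences also fail. Different sites cannot read the passages differently, because this is a single-centre study. An expected count of one or more pregnancies would need a failure rate well above the criterion's ceiling, and the documents give none. Nor do they give a failure rate for condoms or any other listed method, so they cannot show that an example in section 6.1 misses the 1% standard. The description of hormonal methods there is a wording slip and carries no weight here.

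**Conclusion.** The point holds as a moderate safety matter. Sections 1, 6.2, 7.3 and 9.5 do not give one position on what follows when a pregnancy becomes known during device use, and section 9.5 does not distinguish the device from follow-up. Between Visit 1 and the end of treatment no contact is scheduled to ask, so the week-6 extension can be agreed as written without pregnancy status being raised.

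The event is uncommon but plausible. The main estimate is about 0.08 to 0.28 expected pregnancies, an 8% to 24% chance of at least one; if everyone stops at six weeks it falls to 0.04 to 0.14, or 4% to 13%. These figures rest on the criterion's 1% ceiling, full recruitment, no early stopping of the device and an assumed 30% to 100% share of child-bearing potential. They show scale only. The textual finding does not depend on them.

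**What to change.** Two changes.

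1. The sponsor and investigator should reconcile sections 1, 6.2, 7.3 and 9.5 into one stated position, given separately for device use and for follow-up assessments, once a pregnancy becomes known. Which position is right is a clinical matter for them, and none is proposed here. The revised section 9.5 can name who applies it.

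2. Add a pregnancy-status question, for participants of child-bearing potential, to the calls already scheduled while the device is in use. At week 6 it should come before continuation is agreed. Mark it in the section 7.6 table and on the CRF. Whichever position is kept can then be applied.

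The cost is protocol wording, a CRF item and one question per existing call. No visit or procedure is added, and sample size and analysis are unchanged.
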